Appendix A

1. Introduction

This document details the proposed presentation and analysis for the main paper(s) reporting results from the Chartered Society of Physiotherapy (CSP) Charitable Trust funded OPTIN trial; a prospective, multicentre, individually randomised, controlled, superiority trial with blinded outcome assessment. This Statistical Analysis Plan (SAP) will not detail the analysis approach to two of the sub-studies of the OPTIN trial, the qualitative and health economic analyses. The approach to the analysis of the minimal clinically important difference (MCID) of two key outcomes is included Appendix A.

The results reported in the main trial papers should follow the strategy below. Subsequent analyses of a more exploratory nature will not be bound by this strategy but are expected to follow the broad principles laid down here. The principles are not intended to curtail exploratory analysis (for example, to decide cut points for categorisation of continuous variables), nor to prohibit accepted practices (for example, data transformation prior to analysis), but they are intended to establish the rules that will be followed, as closely as possible, when analysing and reporting the trial. This document follows the published guidelines regarding the content of statistical analysis plans for clinical trials [1].

The analysis strategy will be available on request when the principal papers are submitted for publication in a journal. Suggestions for subsequent analyses by journal editors or referees, will be considered carefully, and carried out as far as possible in line with the principles of this analysis strategy; if reported, the source of the suggestion will be acknowledged.

Any deviations from the statistical analysis plan will be described and justified in the final report of the trial. The analysis will be carried out by an identified, experienced lead member of the research team (MN) and supervised by an appropriately qualified and experienced statistician (RK), who will ensure the integrity of the data during their processing. The MCID analysis will be carried out by EH. Examples of such procedures include quality control and evaluation procedures.

1.2 Abbreviations

٨F	Adverse event
CI	Confidence Interval
CRF	Case Report Form
EARS-B	Exercise Adherence Rating Scale - part B
EQ-5D-5L	EuroQoL-5 dimensions- 5 level questionnaire
FES-I	Falls Efficacy Scale International
FR	Functional Reach Test
GRC	Global Rating of Change Scale
IQR	Interquartile range
ITT	Intention to treat
MCID	Minimal Clinically Important Difference
NHS	National Health Service
NDORMS	Nuffield Department of Orthopaedics, Rheumatology and Musculoskeletal Sciences
NPRS	Numeric Pain Rating Scale
OPTIN	OsteoPorosis Tailored exercise adherence INtervention
PEQ	Personalised Exercise Questionnaire
QUALEFFO-41	Quality of life for Osteoporosis Questionnaire-41
QoL	Quality of life
RCT	Randomised controlled trial
R&D	NHS Trust Research and Development Department
SAE	Serious Adverse Event

SEE	Self-Efficacy for Exercise scale
6MW	Six-minute walk test
SD	Standard Deviation
SAP	Statistical Analysis Plan
TUG	Timed Up and Go test
TLS	Timed Loaded Standing test
TRC	Trial Research Clinician
VFF	Vertebral Fragility Fracture
wFCI	Weighted Functional Comorbidity Index

2. Background and Objectives

2.1 Background

Vertebral fragility fractures (VFFs) affect at least 20% of older adults in the UK and present a significant health and socioeconomic burden.[2] They are associated with osteoporosis, a progressive systemic skeletal disorder characterised by low bone mass and deterioration in bone microarchitecture that increases bone fragility and fracture risk. VFFs can be difficult to detect, some are initially asymptomatic, but all are associated with an increased risk of mortality in the year post fracture and significantly increase the risk of further fractures.[2, 3] Symptoms become more likely as the number of fractures increase and include back pain, low mood, fatigue, functional disability and decreased quality of life (QoL) which can persist long term.[2-4] Vertebral fractures cause spinal deformity e.g., height loss and excess spinal curvature or thoracic hyperkyphosis. This can restrict pulmonary function, cause abdominal problems, and increase the risk of sustaining further vertebral fractures and of balance deficits, falls and non-vertebral fractures.[2-4] Without treatment, progression and functional decline are expected.[2]

Conservative treatment for osteoporosis includes bone protective medications and lifestyle adaptations.[3] Guidelines recommend people with osteoporosis keep active and exercise to slow the rate of bone loss, to maintain muscle strength and physical function and to prevent falls and further fractures.[2-5] Multiple randomized controlled trials (RCTs) have investigated the efficacy of exercise for people with VFFs and reported short-term, post-treatment benefits to pain, strength, spinal posture, balance, fear-of-falling, mobility and QoL. [4-6] A Cochrane systematic review in 2019 concluded there is moderate-quality evidence that exercise improves physical function.[4] However, treatment effects are often small and difficult to sustain. [4, 6] Adherence, or the extent to which patients engage in treatment, has been identified as an important issue by many studies, with adherence to clinic-based exercise protocols often around 50% and lower for unsupervised home exercise. [4-7] Partial or non-adherence is associated with worse outcomes and conversely higher adherence with better outcomes. [4, 6, 7] Adherence is a critical consideration because it affects exercise dose. For example, in the PROVE trial benefits associated with exercise at 4 months were not sustained at 12 months, whilst those who attended more sessions experienced better outcomes.[6] Higher adherence has been associated with greater treatment effects but studies monitoring adherence show exercise compliance declines after supervised interventions cease. [7, 8] When assessing intervention efficacy, it is also important to know the minimal clinically important difference (MCID) of any outcome measure in the population concerned, which is defined as the smallest difference in score which a patient perceives as beneficial.[9] A recent Cochrane review identified the Quality-of-Life Questionnaire (QUALEFFO-41) and the Timed Up and Go (TUG) test as important outcome measures targeted by exercise interventions in people with VFFs and also recognised that their MCIDs were unknown.[4]

2.2 Hypothesis and Study Objectives

Hypothesis: Interventions that support patients in adhering to exercise during treatment and for longer self-management on completion of their episode of physiotherapy exercise rehabilitation will increase the efficacy of exercise rehabilitation and benefit older adults with VFF and back pain.

	Objectives	Outcome Measures and Endpoints
Primary	To compare physiotherapy exercise rehabilitation with adherence support with physiotherapy exercise rehabilitation alone in terms of its effects on lower limb strength, walking and balance.	 Primary endpoint, 12 months post randomisation. Primary outcome: Timed Up and Go (TUG) test of lower limb strength, walking and balance (seconds).[10]
Secondary	To compare physiotherapy exercise rehabilitation with adherence support with physiotherapy exercise rehabilitation alone in terms of its effects on: Physical function (balance, strength, pain, spinal curvature, mobility) Quality of life	 Secondary endpoints 4, 8 months post-randomisation Secondary outcomes: QUALEFFO-41: disease specific, self-report QoL questionnaire, 5 sub-scales and total score, each normalised (0-100). Higher better QoL [11] Falls Efficacy Scale International (FES-I): self-report falls concern, 16 items, each 4 points, total (16-64), higher score more concern.[12] Numeric pain rating scale (NPRS): self-report back pain intensity (0–10) higher greater pain.

nts
ľ

	Fear of falling Exercise self-efficacy Exercise adherence	 Timed Loaded Standing (TLS) test of back muscle endurance, timed (seconds) [13] Functional Reach (FR): dynamic standing balance test, maximum distance reached (cm).[14] 6-minute walk (6MW); functional walking capacity distance walked in 6 minutes (metres).[15] Grip strength (kg); measured with hand-held dynamometer, mean 3 trials each hand.[16] Thoracic kyphosis; measured with a flexicurve, a non-radiological measure of spinal curve (degrees).[17] Falls number/ nature/ outcome: prospective log. Exercise self-efficacy scale (SEE) – 9 items, each 10 points, scores summed (0-90). Higher scores = greater self-efficacy. [18] Exercise adherence: Exercise Adherence Rating Scale (EARS), 6 items, each 5 points, higher more adherence. Session attendance. [19] Adverse events: number/ nature prospective log.
Exploratory	To determine the minimally important clinical difference (MCID) of the TUG test and the QUALEFFO-41 after physiotherapy in patients with VFFs and back pain.	 At 4 months post randomisation TUG QUALEFFO-41 TLS EQ-5D-5L, generic measure of health related QoL, 5 domains, 5-point. [20] Global rating of change (GRC) scale: patient perspective of change rated on 7-point ordinal scale, higher scores more positive change. [21]

3. Study Methods

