Fall in past year ^b			
Needed medical attention			
Participants falling ^a			
1.Frequently (\geq 1/ week)			
2.Occasionally (\leq 1/ month)			
3. Rarely (≤ 1/ year)			
TUG (s) ^ь			
QUALEFFO-41 Total (points) ^b			

QUALEFFO-41 subscales (points) ^b		
Pain		
Physical Function		
Social Function		
General Health		
Mental Health		
Thoracic kyphosis (degrees) ^b		
Grip dominant hand (kg) ^b		
6MW (m) ^ь		
6MW exertion CR10-RPE (0-10) ^b		
Legs		
Breathing		
FR (cm) ^b		
TLS (s) ^b		
FES-I ^b		
SEE ^b		

a: binary and categorical data: n (%), b: continuous data: mean (SD), range or median (25-75% quartiles), range in either case the number of participants providing data will also be reported

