5.6 Reliability

To ensure consistency and reliability of data processing, validation checks will be conducted. This will include checking for duplicate records, checking for missing data, checking the validated values for implausible values and validating potential outliers, and checking that data has been imported into statistical packages correctly. This will involve records from each site. Calculations and processes performed by computer e.g., QUALEFFO-41 calculations will be checked by hand calculations. These checks will be performed for 25 participants randomly sampled from the dataset. Clarification will be sought by comparing electronic datasets with case report forms.

6. Analysis

6.1 Methods used for analysis of primary outcome.

We will plot and display TUG data at all time points: 0, 4, 8 and 12-months to consider patterns of change over time and any outliers. At 12-months post-randomisation the two treatment groups will be compared on the primary outcome of the TUG measure using a multivariate linear regression model adjusting for recruiting centre (stratification factor), age at baseline and baseline TUG score. An unadjusted t-test will also be undertaken. As the TUG is recorded at 4 months and 8 months after randomisation as well, an additional analysis utilising all time points using multi-level modelling and including a treatment by time interaction, if appropriate, will be undertaken. For each of these models, the assumption of approximate normality will be assessed by examining the residuals. If this assumption is not met the first approach will be to consider a transformation to achieve normality. If this is not possible, the two groups will be compared using non-parametric methods (e.g., Mann-Whitney U-test). This analysis will be unadjusted and will consider each time point separately.

TUG (seconds)*	Intervention Mean (SD)	Control Mean (SD)	Mean difference (95% Cl)	p-value
Unadjusted 12- months				
Adjusted for baseline, centre and age				
Supporting analyse	25			
Repeated measure	S			
4 months				
8 months				
12 months				
12 months (per protocol)				

Table 11: Analysis of primary endpoint, TUG test change at 12-months

* A negative change corresponds to a better result at 12-months

6.2 Methods used for analysis of secondary outcomes.

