Appendix A.

MCID sub-study statistical analysis plan

The aim of this sub-study is to estimate the MCID of the TUG test and the QUALEFFO-41 questionnaire. In addition to the key outcome measures (TUG and QUALEFFO-41), the following variables will be used as anchors:

TUG test anchors:

- 1. Global rating change (GRC) scale of walking and balance self-reported rating at 4 months
- 2. Timed Loaded Standing (TLS) test change between scores at 4 months and baseline
- 3. Physical Function (PF) domain of QUALEFFO-41 change between scores at 4 months and baseline.

QUALEFFO-41 anchors:

- 1. GRC scale of quality of life self-reported rating at 4 months
- 2. TLS test change between scores at 4 months and baseline
- 3. EQ-5D-5L change between overall health scale at 4 months and baseline

Participants will be included in the analysis if they have complete baseline and 4-month data for target outcomes and their respective anchors variables. For this sub-group we will perform descriptive statistics (mean and standard deviation (SD), median and interquartile range (IQR), or percentage, where appropriate) for sex, age, height, weight, BMI, comorbidities score, BMD, and T-score lumbar spine.

We will then perform multiple Pearson's correlation analyses for the key outcome measures and each of their corresponding anchors. Anchors that do not show at least a moderate correlative relationship (r>0.4) with their key outcome measure will not be included in further MCID analyses.

We will calculate the change between 4-month scores and baseline for both key outcome measures and eligible anchor variables, excluding GRC scales as they are self-reported only at 4 months.

From the 4-month GRC scores and the change scores calculated from the other anchor variables, we will dichotomise data into 'responder' or 'non-responder' based on the following:

- a) GRC is a 7-point scale: -3 (much worse), -2 (moderately worse), -1 (a little worse), 0 (no change), 1 (a little better), 2 (moderately better), 3 (much better); scores >0 will be labelled as a 'responder' and scores ≤0 labelled as a 'non-responder'.
- b) TLS is a strength test where longer duration indicates stronger musculature; calculated change scores >0 seconds will be labelled as a 'responder' and ≤0 seconds labelled as a 'nonresponder'.

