- c) PF domain of the QUALEFFO-41 is a questionnaire where a *lower* score indicates better physical aspects of quality of life; calculated change scores <0 will be labelled as a 'responder' and scores ≥0 labelled as a 'non-responder'.

d) ED5Q overall health scale is reported on a visual analogue scale from 0-100, where 100 indicates best health; calculated change scores >0 will be labelled as a 'responder' and scores ≤0 will be labelled as a 'non-responder'.

Based on these dichotomised data, we will perform anchor-based analyses for the TUG and QUALEFFO-41 using each eligible corresponding anchor variable. Methods of anchor-based analysis will include:

- a) Average Change (AC) the average score change of the responders, according to the anchor.
- b) Change Difference (CD) the average score of change of responders (according to the anchor) minus the average score of change of non-responders.
- c) Receiver-operating characteristic (ROC) analysis a plot of sensitivity against specificity using dichotomised data from each anchor. We will use Youden's J statistic and Euclidean distance to determine the optimal cut-off values, and also calculate the area under the curve (AUC).

In addition to the anchor-based methods, we will estimate the MCID with distribution-based analysis by calculating 0.5SD of the TUG and QUALEFFO-41 change scores (between baseline and 4 months).

Key outcome	Corresponding	Method of analysis				
measure	anchor	AC (s)	CD (s)	ROC (s)	0.5 SD (s)	
	GRC					
TUG	PF					
	TLS					
	GRC					
QUALEFFO-41	EQ-5D					
	TLS					

Example Table A: MCID values for key outcome measures

Example Table C: ROC analyses

Key outcome measure	Corresponding anchor	Youden's J statistic	Euclidean distance	AUC
TUG	GRC			
	PF			
	TLS			
QUALEFFO-41	GRC			
	EQ-5D			
	TLS

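### QUALEFFO-41 Physical Function runs higher-is-better in SAP section 2.2 and lower-is-better in Appendix A, so a benefit could be read as harm or responders reversed

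*SAP*

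**What the plan says.** The objectives table in SAP section 2.2 lists the QUALEFFO-41 as a secondary outcome with "5 sub-scales and total score, each normalised (0-100). Higher better QoL". Table 10 (section 5.5) sets out the five sub-scales as Pain, Physical Function, Social Function, General Health and Mental Health.

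Appendix A uses Physical Function as the third anchor for the TUG: "Physical Function (PF) domain of QUALEFFO-41 change between scores at 4 months and baseline". Item c of its responder rules then says: "PF domain of the QUALEFFO-41 is a questionnaire where a *lower* score indicates better physical aspects of quality of life". The rule that follows is "calculated change scores <0 will be labelled as a 'responder", with zero or positive change making a non-responder.

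For the TUG, Table 11 (section 6.1) carries a direction note: "A negative change corresponds to a better result at 12-months". Table 12 (section 6.2) reports the QUALEFFO-41 total and five sub-scales as mean differences without one. No other part of the SAP states a QUALEFFO-41 direction, and none describes reversing the scores for the sub-study.

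**The concern.** Both statements are current text and they describe the same sub-scale, so at least one is wrong. The QUALEFFO-41 has three uses in the plan: it is the disease-specific quality-of-life outcome, it is one of the two MCID targets, and its Physical Function domain is an anchor for the MCID of the other target, the TUG.

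Two errors could follow. If the scores run lower-is-better, anyone who interprets Table 12 by section 2.2 reports a benefit as harm, or the reverse. If they run higher-is-better, the Appendix A rule reverses the responder groups on the Physical Function anchor. The Introduction gives the main analysis and the MCID analysis to different analysts, so each could follow a different statement in good faith.

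**Working it through.** The plan has no figure to reproduce here. The check is to set the statements side by side and follow each possibility through.

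**Statements on the Physical Function score**

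| Place | Direction |
|---|---|
| Section 2.2 (each sub-scale and the total) | higher = better |
| Appendix A, item c | lower = better; change < 0 = responder |

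Table 10 confirms that Physical Function is one of the sub-scales covered by section 2.2.

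**Effect on Table 12.** Reversing a 0-100 scale replaces the score S with 100 − S.
- The constant cancels in a group contrast, so a mean difference D becomes −D, and a 95% CI of (L, U) becomes (−U, −L).
- In the adjusted model the baseline covariate is reversed too, and the treatment coefficient again only changes sign.
- Magnitude and two-sided p-value stay the same. This holds for the linear models on the untransformed score.
- The direction stated in the plan is therefore all that tells the reader which arm did better.

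**Effect on the Physical Function anchor.** Change becomes −change, so the rule change < 0 selects the opposite people. Every participant with a non-zero change switches label.

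An illustration gives the scale of this. The inputs are assumptions, not figures from the SAP: improvements on TUG and Physical Function are bivariate normal, with mean m = 0.3 SD on each and correlation r.
- Share improving on Physical Function: Φ(0.3) = 0.618. The rule labels 62% as responders if lower is better. If higher is better, it labels the 38% who worsened.
- TUG change difference (responders minus non-responders) if lower is better: −r × φ(0.3) / [Φ(0.3)(1 − Φ(0.3))] = −r × 0.3814 / (0.618 × 0.382) = −r × 1.615. If higher is better, the sign is reversed.

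| r | Formula, absolute value | Simulated, lower better | Simulated, higher better |
|---|---|---|---|
| 0.3 | 0.48 | −0.48 SD | +0.48 SD |
| 0.5 | 0.81 | −0.81 SD | +0.81 SD |
| 0.7 | 1.13 | −1.12 SD | +1.12 SD |

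The simulation used 200,000 draws per row. A negative TUG change is an improvement, so the last column has the wrong sign for an MCID. At r = 0.5 the average TUG change among labelled responders moves from −0.61 SD to +0.20 SD.

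**Effect on anchor eligibility.** Appendix A says: "Anchors that do not show at least a moderate correlative relationship (r>0.4) with their key outcome measure will not be included". As written, the threshold is signed. At r = 0.5 in the illustration, the correlation between TUG change and Physical Function change is +0.50 if lower is better (anchor kept) and −0.50 if higher is better (anchor dropped).

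The same applies to the QUALEFFO-41 as a target. Its anchors (GRC, TLS and the EQ-5D-5L overall health scale) are all higher-is-better. If the total is lower-is-better, all three correlations should be negative, and a literal reading would drop every anchor.

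**The case against.** The best counter-arguments concern scope and consequence, since the contradiction itself cannot be explained away.

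- **Only one sub-scale is in explicit conflict.** This stands. Appendix A gives no direction for the total or the other four sub-scales. The doubt about them arises because one statement in section 2.2 covers all six scores and is contradicted for one.
- **The responder problem is narrow.** This also stands. Physical Function is one of three TUG anchors in an exploratory objective, and the QUALEFFO-41 total is never dichotomised. Appendix A is coherent in itself: its rule matches its stated direction. If section 2.2 is the wrong statement, no responder label changes, but the Table 12 reading is then misdirected.
- **A reversal would be noticed.** This stands only in part. A literal r > 0.4 screen would drop a reversed Physical Function anchor. However, TUG (lower better) should correlate negatively with GRC and TLS (both higher better) however the QUALEFFO-41 runs. A literal rule would lose those anchors too, so an absolute value may be intended, and a reversed anchor would then pass. Wrong-signed results might raise suspicion, but the plan should not depend on that. The hand checks in section 5.6, on 25 participants, test the calculation and not which direction is good.
- **No estimate changes, and this is a secondary outcome.** True for the between-group models. Section 4.1 treats secondary outcomes as supporting the primary result. The risk is in interpretation, where the sign decides what is concluded.
- **The Table 12 footnote is a matter of preference.** Fair. Other measures in Tables 12 and 13 have none either. The note is useful here because the only stated guide to QUALEFFO-41 direction is in dispute.

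**Conclusion.** The point holds and should be corrected before analysis. Section 2.2 and Appendix A give opposite directions for QUALEFFO-41 Physical Function, and the SAP alone does not settle which is right.

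The explicit conflict affects one sub-scale and the responder label of every participant with a non-zero change on it. By implication, it leaves the reading of all six QUALEFFO-41 contrasts in Table 12 in doubt, along with the signs of the QUALEFFO-41 average change, change difference and ROC cut-off. Which of these goes wrong depends on which statement is wrong. Absolute effect sizes and p-values in the linear models are unaffected, as are the 12-month TUG comparison and the sample size. The simulated figures rest on assumed inputs and only illustrate the reversal; the contradiction does not depend on them.

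**What to change.** 1. Check the direction produced by the scoring algorithm the trial uses, from the source cited for the QUALEFFO-41 in section 2.2.
2. State that direction in section 2.2 for the total and for each of the five sub-scales.
3. Make item c of Appendix A agree with it, in both the description and the responder inequality. State there which sign of QUALEFFO-41 change means improvement.
4. Add a direction note for the QUALEFFO-41 to Table 12, as Table 11 has for the TUG.
5. While editing Appendix A, say whether the 0.4 correlation threshold applies to the absolute value.

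The cost is about one line each in section 2.2, Table 12 and Appendix A. Data collection, models and sample size stay as they are.
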